1.3 Assessment and management of risk

The co-CIs will ensure, through the TSC, that adequate systems are in place for monitoring the quality of the study (compliance with GCP) and appropriate expedited and routine reports of adverse events, to a level appropriate to the risk assessment of the study.

Women will be informed of possible benefits and known risks (including known complications) of both treatment policies in the trial by means of a Participant Information Leaflet, discussion with the local Research Nurses and their own Consultant Gynaecologist. Both treatment policies (medical and surgery treatment) are routinely used within the NHS. We do not anticipate that participants will run additional risks by participating in DIAMOND. They will sign a consent form approved by the Ethics Committee. They will be consented to participating in the study with follow up, being randomised, being contacted in the future about this and other research including electronic tracing using NHS data, and data linkage with computerised NHS data sources. Women who are not able or not willing to be randomised will not be recruited.

2. Trial Aims and Objectives

The primary aim of the trial is to compare the clinical and cost-effectiveness of medical treatment versus laparoscopic surgery for the management of deep endometriosis.

The research question to be addressed is: What is the clinical and cost-effectiveness of medical management alone versus laparoscopic surgery (with or without adjuvant medical treatment) in women with deep endometriosis?

2.1 Primary objectives

The primary objectives are:

- To compare medical (hormonal) treatment with laparoscopic surgery for deep endometriosis (with or without adjuvant medical treatment) in terms of condition specific quality of life measured using the pain domain of the Endometriosis Health Profile-30 (EHP-30) and health status using EQ-5D-5L at 18 months after randomisation.
- To assess the cost-effectiveness of medical (hormonal) treatment with laparoscopic surgery (with or without adjuvant medical treatment) for deep endometriosis in terms of the incremental cost to the health service per QALY gained at 18 months post randomisation and modelled up to the time of menopause (QALYs derived from participant responses to the EQ-5D-5L).

2.2 Secondary objectives

To compare medical (hormonal) treatment with laparoscopic surgery for deep endometriosis (with or without adjuvant medical treatment) in terms of:

- satisfaction;
- pain;
- condition specific quality of life and participants' functional health and well-being (EHP-30 and core domains at 12 weeks and 12- and 18-months post-randomisation);
- generic quality of life;
- need for further medical treatment and gynaecological surgery;
- serious adverse events and major surgical complications (Clavien Dindo grades 3-5 ²⁶);
- discontinuation of randomised treatment (with reasons for change);
- sexual function (EHP-30 + Section C questionnaire);
- occupational outcomes;
- reproductive outcomes (pregnancy, live birth and other obstetric outcomes);
- indirect costs due to loss of productivity.
- number of women in the medical treatment arm who go on to have surgery and vice versa

The outcomes for the primary and secondary objectives are fully described in section 6 of this protocol.

[figure not shown]
2.3 Qualitative sub-study

There is an embedded qualitative sub-study in DIAMOND (see Appendix 1). One to one interviews (either face to face or via telephone or video call) with women and staff from recruiting centres will be conducted to explore the patient experience of both the trial and the interventions. The aim of the qualitative sub-study is to inform delivery of the study and facilitate problem solving during an internal pilot as well as the main phase of the trial and to provide timely feedback and improve successful recruitment and delivery of the DIAMOND trial. Qualitative data will also be used to explore the experiences of women randomised to different pathways of care. In sites where recruitment is problematic, we will audio record consultations to identify how recruitment consultations are framed.

3. Trial Design

This is a multi-centre randomised controlled trial, with an internal pilot phase, to compare medical management alone versus planned laparoscopic surgery (first attempt at definitive surgery) with or without adjuvant medical treatment) in women with deep endometriosis. The trial structure is shown in Figure 1 (Flow Diagram). The internal pilot will monitor recruitment and assess the willingness of patients to participate in DIAMOND. The embedded qualitative sub-study is described in Appendix 2.

Figure 1 Flow diagram

3.1 Interventions to be evaluated

i) Medical management:

This will involve hormonal treatment for 18 months. The choice of hormonal medication will be at the discretion of the treating clinician in discussion with the participating woman, avoiding any treatment which has either failed or caused unacceptable side effects in the past. Any of the following preparations can be used: the combined contraceptive pill/patch (COCP), progestogen only preparations (oral tablets), depot injections (depot medroxyprogesterone acetate (DMPA), subcutaneous implants (e.g. Nexplanon) or intrauterine systems (levonorgestrel intrauterine systems (LNG-IUS)), danazol and gonadotrophin releasing hormone (GnRH) analogues with add back hormone replacement therapy (HRT). Women on hormonal treatment can receive additional neuromodulator drugs, analgesics and other interventions for pain relief. Medical treatment will be prescribed in line with normal and accepted clinical practice, as recommended by NICE guidelines on management of endometriosis⁷ in the UK

ii) Laparoscopic Surgery (with or without adjuvant medical treatment):

A laparoscopic approach will be used to treat DE but the choice of energy modalities and the need for concomitant hysterectomy and/or oophorectomy will be left to the discretion of the surgeon in consultation with their patient. Surgery will involve division of dense adhesions to separate affected pelvic structures, restore normal anatomy and removal of all endometriotic deposits, including deep nodules. Excision of DE is achieved using laparoscopic instruments such as scissors, hooks and ultrasonic scalpels along with a variety of energy modalities including electricity and ultrasound. If adjuvant medical management is needed, the same medical options used in the medical treatment arm (see below) will be utilised including hormones, neuromodulators and pain relief medication. For pragmatic reasons, changes to medical treatment used prior to surgery will be accepted, in line with NICE guidelines⁷.

Further details about the intervention are provided in section 5.1.

4. Trial Recruitment

4.1 Trial population

We will recruit 400 women aged between 18-49 years presenting with pelvic pain associated with DE who are suitable for either medical or surgical management.

4.2 Setting

This trial will take place in British Society for Gynaecology Endoscopy (BSGE) accredited and provisional UK Endometriosis centres where all operations will be performed. This will allow comparison of optimal surgery by endometriosis specialists with those allocated medical treatment.

4.3 Inclusion and exclusion criteria

Inclusion criteria:

- Women aged 18–49 years old seeking treatment for pain
- Confirmed deep endometriosis (laparoscopic or other routinely used investigative radiology technique)
- Suitable for either medical or surgical management
- Able and willing to give informed consent to participate and to participate in study procedures (*There are provisions within the protocol for recording consent from patients who are not able to read or write (but who have capacity and who can speak English sufficiently to understand the information being provided orally); see section 4.7*)

Exclusion criteria:

- Unfit for laparoscopic surgery
- Have used or currently using GnRH analogues without satisfactory relief of pain symptoms
- Previous bilateral oophorectomy
- Previous surgery for deep endometriosis
- Actively trying to conceive
- Confirmed bowel stenosis
- Hydronephrosis or hydroureter caused by ureteric stenosis
- Endometrioma > 5cm in diameter
- Women with preference for hormonal medical or surgical treatment
- Current pregnancy or breast feeding

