In a recent survey of 66 women with endometriosis undertaken by the applicants in conjunction with Endometriosis UK, 47% of responders stated that they were willing to be randomised to either medical or surgical treatment and most (74%) felt that relief of pain and quality of life were the most important outcomes. The best time point for the assessment of symptoms was felt to be 6, 12 or 24 months after starting treatment by 42%, 35% and 17% women respectively, while 6% felt that outcomes should be assessed at several points in time.

Of 79 specialist clinicians surveyed by the British Society for Gynaecological Endoscopy, 43% felt there was insufficient evidence to inform decision making in DE management and 94% were willing to randomise their patients to either a surgical or medical pathway. Most (64%) considered both pain and quality of life to be the most important outcome measures; with 3% prioritising pain and 34% quality of life. Post treatment, the optimal follow-up period was felt to be 12 and 24 months by 44% and 36% respectively, while 20% of respondents favoured measurements at multiple time points.

The current clinical pathway for management of women with pain due to DE involves initial medical management using a variety of hormonal agents, but ultimately many women go on to have surgery. Laparoscopic excision of endometriosis has been shown to improve pain symptoms in DE¹³ and surgery has been the traditional approach favoured by many clinicians who believe that medical treatment cannot reverse pelvic scarring caused by the condition.¹⁴⁻¹⁶ While surgery is the only option in women with mechanical obstruction of the bowel or ureters, long-term hormonal treatment with the aim of shrinking areas of endometriosis have been

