7.2 Baseline

Participants will complete the baseline questionnaire (including EHP-30 + Section C and EQ-5D-5L) prior to randomisation.

The site research team will complete the baseline CRF including information on parity; age, ethnicity, current and previous treatments used for endometriosis associated pain.

At baseline, we will also collect contact details of participants (including postal address, email, home and mobile number) and their contact preferences (see section 7.4) along with details of their GP.

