10.1 Sample size

We need primary outcome data on 320 women at 18 months to detect an 8-point difference for the EHP-30 pain domain for 90% power (two-sided alpha 0.05) assuming a standard deviation of 22 points. The 8-point improvement was decided as a clinically important difference for the Pre-Empt trial²⁵ and has now been accepted for use by all new endometriosis trials to allow consistency and comparison of results and future metanalysis. We have assumed an attrition rate of 20% for the primary outcome, which requires us to randomise 400 women in total. The anticipated attrition rate is based on follow up data from BSGE accredited Units which have a dedicated endometriosis nurse and work to a consistent protocol which includes patient completed post-operative questionnaires at 6 and 12 months. As women with DE are all referred for treatment to dedicated endometriosis centres, they are unlikely to be lost to follow-up or choose to seek treatment elsewhere.

Attrition rates will be monitored to detect differential drop-out, which can bias clinical trial results and reduce the power of the trial to detect important differences.

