10.2 Recruitment rates

Our surveys show that approximately 30 women per centre will undergo surgery for DE annually and at least 40% will be willing to be randomised. The recruitment projection is based on an estimate of 40 active centres contributing 0.8 participants per month over 22 months. This allows for staggered centre set-up and 50% reduced recruitment during the first month of site set up and 50% during the holiday months of June/July, December and April. The first 23

patients will be recruited by month 12 (recruitment month 6), 145 patients by month 18, 289 patients by month 24 and the remaining 111 by month 28, making a total of 401 participants.

The projected recruitment is modelled below in Figure 2.

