11.1 Planned subgroup analyses

We will undertake subgroup analyses by age and presence of recto-vaginal endometriosis. The potential moderating effects of subgroup will be modelled using treatment-by-subgroup interactions. Treatment effects and interactions will be reported with stricter confidence intervals at the 99% level to reflect the exploratory nature of these analyses.

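### Hormonal treatment before entry is recorded at baseline and shapes the contrast under test, but it is in neither the stated primary model nor the planned subgroups

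*Protocol*

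**What the plan says.** - **Eligibility (section 4.3).** The one criterion on earlier hormones is the exclusion "Have used or currently using GnRH analogues without satisfactory relief of pain symptoms". Nothing requires or bars earlier use, or earlier failure, of the combined pill or patch, progestogens, intrauterine systems or danazol.
- **The mix is expected.** Sections 3.1 and 5.1 tell clinicians choosing a hormone to avoid any that has failed or was not tolerated. Section 5.2 foresees women already on hormones when allocated to surgery. Section 1.1 describes usual care: "The current clinical pathway for management of women with pain due to DE involves initial medical management using a variety of hormonal agents".
- **What is being compared.** The trial title and the Trial Summary speak of early surgery. Sections 2 and 3 drop the word and compare medical management with laparoscopic surgery.
- **What is recorded.** Under section 7.2 the baseline CRF includes "current and previous treatments used for endometriosis associated pain".
- **What is analysed.** Minimisation uses site and age band (section 4.8). The primary model has treatment, time, design covariates and the baseline score, with random effects for centre and participant (section 11). On subgroups, section 11.1 says: "We will undertake subgroup analyses by age and presence of recto-vaginal endometriosis". Interactions are reported with 99% intervals.

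**The concern.** For a woman who has never taken hormones, the trial compares a first hormone with surgery. For a woman who has already used one or more, it compares continuing or changing hormones with surgery, and any agent that has failed is ruled out for her. Treatment history therefore partly determines what the medical arm can offer, which makes it a direct candidate for modifying the treatment effect.

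The primary analysis gives one average over these women. If the effect differs by history, the planned analysis will not show it. A reader told about early surgery will not know whether the result describes women at the start of the pathway or women well along it. There is also no washout, so the baseline EHP-30 pain score is taken on hormones in some women and off them in others. The stated model adjusts for the score but not for that difference.

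**Working it through.** **1. The protocol's own figure.** Section 10.1 says "We need primary outcome data on 320 women at 18 months", in order "to detect an 8-point difference for the EHP-30 pain domain for 90% power (two-sided alpha 0.05) assuming a standard deviation of 22 points".

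Per arm: n = 2 × [22 × (1.960 + 1.2816) / 8]² ≈ 158.9, rounded up to 159, so 318 in total against 320 stated. With 160 per arm, power is 90.2%. Allowing for 20% attrition, 320 / 0.8 = 400. The sample size reproduces, and nothing below changes it.

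**2. What pooling can hide.** The protocol gives no share of hormone-naive women, so the shares here are assumptions. Suppose, for illustration, that surgery's advantage is 8 points in previously treated women and 0 in naive women. Then pooled effect = 8 × (1 − naive share), and power is for 160 per arm, SD 22, two-sided alpha 0.05.

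| Naive share | Pooled effect | Power |
|---|---|---|
| 10% | 7.2 | 83% |
| 20% | 6.4 | 74% |
| 30% | 5.6 | 62% |
| 50% | 4.0 | 37% |

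Conversely, a pooled 8 points fits 8 in both groups, or 16 and 0 at an even split (0.5 × 16 + 0.5 × 0 = 8). The pooled estimate cannot separate these.

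**3. What a never-versus-ever subgroup could show.** With n₁ and n₂ women per arm in the two groups, the interaction has SE = 22 × √(2/n₁ + 2/n₂), and the 99% half-width is 2.576 × SE. For example, at 30% naive n₁ = 48 and n₂ = 112, so SE = 22 × √(0.0417 + 0.0179) = 5.37. Power is for a test at the 99% level.

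| Naive share | n₁ / n₂ per arm | SE | 99% half-width | Power, 8 points | Power, 16 points |
|---|---|---|---|---|---|
| 10% | 16 / 144 | 8.20 | 21.1 | 5% | 27% |
| 20% | 32 / 128 | 6.15 | 15.8 | 10% | 51% |
| 30% | 48 / 112 | 5.37 | 13.8 | 14% | 66% |
| 50% | 80 / 80 | 4.92 | 12.7 | 17% | 75% |

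The even split is the best case. Three equal levels would leave 320 / 6 = 53.3 women per arm per level, with a pairwise SE of 22 × √(4/53.3) = 6.0 and a half-width of 15.5. That is why never versus ever is the better contrast for the interaction. Balanced groups would need about 1,272 analysed women for 90% power on an 8-point interaction at two-sided alpha 0.05.

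These figures use the unadjusted SD of 22. Adjustment for the baseline score would narrow the intervals by an amount that the protocol gives no means to compute.

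**4. The covariate.** The baseline EHP-30 score is already in the model. Nothing in the protocol shows how much further 18-month variance treatment status would explain, so the precision gain is unknown.

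**The case against.** The strongest case for leaving the plan alone has four parts.

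- **Broad entry is deliberate.** Section 1.2 sets this trial apart from a narrower one by its wide entry criteria. Section 4.3 requires suitability for either treatment and excludes women with a preference. This stands: entry is not a defect, and randomisation keeps the pooled comparison unbiased.
- **'Early' need not mean before hormones.** The Trial Summary links it to a planned first attempt at definitive surgery, and the objectives in section 2 omit it. This stands in part. The word is still in the trial title, against a usual pathway of hormones first, so readers will want to know whom it covers.
- **An extra covariate or exploratory subgroup is ordinary SAP content.** Section 11 defers full details to the SAP, which is not at hand and may add them. But this protocol itself states the model and names the subgroups, and it leaves out a modifier that it collects.
- **The interaction is weakly powered.** True, and the 99% rule already treats the named subgroups as exploratory for the same kind of reason.

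Three stronger readings are tempting and are not supported. A reader might infer that most recruits will be women whose hormones failed, from "approximately 30 women per centre will undergo surgery for DE annually and at least 40% will be willing to be randomised". That is a volume estimate for the recruitment projection, and section 4.5 recruits from clinics where both options are still being discussed. A reader might infer that the new subgroup would separate early surgery from surgery after failure. Section 7.2 records treatments used and mentions neither response nor reason for stopping. A reader might also infer that the primary estimate is biased, which randomisation rules out.

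**Conclusion.** The point holds as one of interpretation and pre-specification. Hormone history shapes the contrast, is already collected, and is absent from the minimisation factors, the stated model and the named subgroups. As planned, the analysis cannot show whether the effect varies with prior hormone use, or to whom a statement about early surgery applies.

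The size depends on an unknown naive share. Across assumed shares of 10% to 50%, the interaction would have a 99% half-width of 21.1 down to 12.7 points and 5% to 17% power for 8 points. It would therefore be descriptive, able at best to suggest a large contrast. Ever used is a proxy for failed and does not establish failure unless the CRF records response. The change is worth making, but the validity of the primary comparison does not depend on it.

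**What to change.** Before any outcome data are seen by arm:

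1. Derive hormonal treatment status at entry (never / past / current) from the baseline CRF, and add it as a fixed effect in the primary model in section 11.
2. Add never versus ever used hormones as a third exploratory subgroup in section 11.1, by treatment-by-subgroup interaction under the same 99% interval rule.
3. Tabulate the three-level status by arm with the baseline characteristics.
4. Word any conclusion about early surgery for the women actually enrolled, using that table.
5. State that ever used is a proxy. Check whether the CRF captures response or reason for stopping. If it does, define failure in advance and report it descriptively.

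The cost is protocol and SAP wording, two degrees of freedom in the model and one more low-powered exploratory interaction. Eligibility, treatment, minimisation, visits and sample size (320 analysed, 400 randomised) are unchanged.

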4.4 Co-enrolment

Participants will be permitted to take part in non-interventional studies (e.g. questionnaire studies). Those enrolled in the active intervention phase of another gynaecological or other interventional trial will be excluded but they would be eligible for inclusion if they are now in the long term follow up phase of such trials. Patients who were in PRE-EMPT or other relevant endometriosis trials, who have completed the active intervention phase and meet the eligibility criteria can be considered for inclusion.

4.5 Identifying and approaching participants

Women will be recruited from endometriosis clinics and general gynaecology clinics of hospitals which are BSGE accredited and provisional endometriosis centres, although peripheral hospitals referring women with confirmed DE to endometriosis centres (accredited and provisional) for further assessment and discussion about medical and/or surgical treatment, can approach potential participants about the study. Restricting recruitment to BSGE accredited and provisional endometriosis centres has several advantages including:

- Access to dedicated weekly endometriosis clinics run by gynaecologists who are likely to be able to access a large pool of eligible participants (>5 per centre per month);
- The ability to offer optimal surgery performed by specialists thus ensuring standardisation of the comparator arm;
- The presence of endometriosis nurse(s) in each centre, who along with research nurse(s) can monitor compliance with medical management, promote recruitment and provide patient support.

Eligible women who are referred with pelvic pain associated with DE may be identified by the DIAMOND research nurse(s) in each centre as a potential participant, prior to their outpatient appointment. Local procedures at the participating hospitals are different and the timing and mode of approach to women and the consent process may vary to accommodate both the specific circumstances at each site and the needs of the women.

Each eligible woman will be given or sent (generally prior to the outpatient clinic appointment or at the clinic) a Participant Information Leaflet (PIL) describing the study and will have the opportunity to read this before deciding whether or not to take part. The gynaecologist who will be providing her clinical care will discuss treatment options and establish eligibility, and women will have the opportunity to discuss the study with the gynaecologist – these consultations may occur face-to-face or virtually using NHS platforms accepted locally. Women can also discuss all aspects of the proposed research with other members of the local clinical team, the Research Nurse, family and friends and, if appropriate, with their GP before deciding if they will take part in the study. Women may decide to participate during an initial (or subsequent) consultation with their gynaecologist or alternatively at home.

If the woman decides to participate at home, they will be sent or given (if initial consultation is face-to-face) the consent form and baseline questionnaire for completion. If the woman agrees

to be contacted at home, she may receive a telephone call from the site Research Nurse to discuss any queries. Women who decide to participate at home may send their completed documents (consent form and baseline questionnaire) through the post to the local team at their treating hospital. All women will have the option to complete the consent form electronically rather than completing a hard copy. Details of the consent discussion, including discussion date, will be recorded.

The PIL and consent form will also refer to the possibility of long-term follow up to determine repeat surgery and pregnancy.

All women who are randomised into the study will be assigned a unique Study Number.

Eligibility will be confirmed by the PI, or by a medically qualified delegate at each recruitment site.

A paper screening log will be kept at site, with limited (non-identifiable) information uploaded onto the study website.

